4.3 Selection of sites

Available recommendations suggest to perform sample size calculation based on indicators with lowest effective sample size (e.g., viral suppression, where effective sample is limited to the HIV positive fraction). However, with the desired level of precision (e.g. less than +/-10%) at the city level, this yields sample sizes which are not feasible, especially in the cities with low HIV prevalence (e.g. Kharkiv). Therefore, it was recommended to consider clustering of cities based on analyses of trends/similarities to ensure a larger sample size.⁹

Prior to 2020, the IBBS in Ukraine were conducted in each administrative unit (N=27), presumably generating a nationally-representative sample, enabling direct comparison of indicators across rounds and analysis of trends.¹⁰ After the resources for surveillance became more limited, the number of participating cities was decreased to 12 in 2020. The selection of cities was made by the national working group, based on epidemiologic and programmatic priorities. Nevertheless, a direct comparison between 2020 and previous rounds is not possible due to the difference in geography and varying sample sizes in cities that participated in each round.

Considering that accurate monitoring of trends in key indicators in IBBS series is at least as important as point estimates, and also following the CDC recommendation (to cluster cities), it is proposed that *a single cluster of cities will be selected for this round and will remain stable* in the next rounds of IBBS. This strategic approach also corresponds to the concept of sentinel surveillance, in which a consistent sample of sites continues to generate data over an extended period of time. As the sentinel

⁹ CDC/DGHT Key Population Surveillance Team and CDC Ukraine Joint Evaluation of IBBS in Ukraine – Nov. 2017

¹⁰ Dumchev, K., Sazonova, Y., Salyuk, T., & Varetska, O. (2018). Trends in HIV prevalence among people injecting drugs, men having sex with men, and female sex workers in Ukraine. *Int J STD AIDS*, 29(13), 1337-1344.

doi:10.1177/0956462418784096

approach implies, selected sites should represent geographically and epidemiologically diverse areas and be most likely to detect emerging behavioral and epidemiologic trends. Given that, the following cities were selected by the national IBBS working group as **sentinel** sites for the 2023 and future rounds of PWID IBBS in Ukraine:

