4.4 Sample size and power calculation

To calculate the sample size, a design effect was empirically estimated in the 2020 IBBS data set using the Gile's SS estimator based on the actual network size in "RDS" package in R v.4.0.5 (Table).

	HIV prevalence				Viral suppression			
	Est.	95% CI LL	95% CI UL	D.Eff.	Est.	95% CI LL	95% CI UL	D.Eff.
Bila Tserkva	16.1%	10.2%	21.9%	3.11	77.7%	66.6%	88.7%	2.39
Dnipro	26.5%	19.8%	33.2%	2.78	68.8%	54.8%	82.6%	3.56
Ivano-Frankivsk	9.3%	5.8%	12.9%	2.61	89.3%	82.8%	96.4%	1.44
Kirovohrad	10.2%	7.0%	13.4%	1.80	74.2%	61.4%	87.3%	2.70

Kryvyi Rih	21.9%	16.1%	27.7%	2.13	70.6%	59.9%	81.1%	1.72
Kyiv	18.2%	12.9%	23.5%	3.27	86.0%	77.0%	95.0%	2.96
Mariupil	30.5%	25.3%	35.6%	2.11	80.9%	72.7%	89.1%	2.21
Mykolaiv	33.2%	27.5%	38.9%	2.88	76.4%	68.3%	84.4%	2.49
Odessa	21.2%	15.3%	27.1%	2.50	80.7%	73.4%	87.9%	1.31
Kharkiv	7.5%	4.1%	11.0%	2.12	90.9%	91.0%	91.0%	-
Khmelnytskyi	29.7%	23.7%	35.7%	2.47	81.9%	74.3%	89.3%	1.91
Cherkasy	38.4%	31.4%	45.6%	2.43	86.5%	80.1%	93.0%	1.61

As shown, the design effect for HIV prevalence ranges from 1.8 to 3.3, and for viral suppression from 1.3 to 3.6. Therefore, a conservative value of 3.0 is used for the following sample size calculation.

The calculation was made for *the single sentinel cluster* sample, with expected HIV prevalence of 21% and 44% viral suppression (combined weighted estimate using 2020 round data for 5 cities and 2017 data for Lviv). Based on the simple asymptotic CI formula,¹¹ 0.05 probability of type I error, anticipated 5% of missing data, and 14% desired precision level for the viral suppression indicator (e.g. 44±7%), the resulting sample size should be 2914.

[figure not shown]
In order to simplify trend analysis across rounds, the total sample will be distributed evenly across participating cities, yielding a rounded target sample size of 500 in each city. This result corresponds to the standard universal sample size used in the US NHBS-IDU.¹² At the city level, assuming the design effect of 3.0 and 5% of missing data (e.g. incomplete data entry, entry errors), a sample size of 500 will provide ~16% precision for a maximally-conservative estimated prevalence for any indicator – 50% (i.e. 50±8%, the interval will be narrower for proportions closer to extremes, either 0 or 100%).

The same target sample size will be used for each additional city (outside the sentinel cluster).

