9.2 Descriptive statistics

Descriptive statistics for all key variables (prevalence of infections, drug use, behaviors, service use, HIV treatment cascade, etc) will include category size (n), population proportions with 95% confidence intervals, means with standard errors or medians with interquartile range. All descriptive statistics including confidence intervals will be calculated using the RDS weights. The total sample estimates will use the RDS weights but will not be additionally weighted due to the equal sample size in each city. When the population size calculation becomes available (see below), additional weighting by population size in each city will be done to obtain estimates for the entire city sample for key variables. Descriptive tables will be disaggregated by city and key demographic characteristics (age group and gender). Visualizations for selected variables and disaggregations will be provided in bar or line charts. The design of tables and charts will take into account the structure of the previous reports on the IBBS findings in Ukraine.

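### The city-level precision of 50±8% is stated for any indicator, but it holds only for indicators measured in the full city sample; for those measured in HIV-positive participants the same inputs give about ±17 points at 21% prevalence

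*Protocol*

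**What the plan says.** Section 4.4 first sizes the sentinel cluster on viral suppression, "with expected HIV prevalence of 21% and 44% viral suppression", with a target of 44±7%, and concludes that "the resulting sample size should be 2914". It spreads this over the cities, "yielding a rounded target sample size of 500 in each city". For a single city, "assuming the design effect of 3.0 and 5% of missing data", it states that "a sample size of 500 will provide ~16% precision for a maximally-conservative estimated prevalence for any indicator". It writes this as 50±8% and adds that the interval narrows for proportions nearer 0 or 100%. No restriction on the denominator is given.

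Section 4.3 takes a different position on viral suppression. It notes that only the HIV-positive fraction of the sample counts, and that "with the desired level of precision (e.g. less than +/-10%) at the city level, this yields sample sizes which are not feasible", naming Kharkiv as an example.

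Section 9.6 defines status knowledge, clinic registration and ART among participants with an HIV-positive rapid test in the survey. Section 9.2 lists the treatment cascade among its key variables and says "Descriptive tables will be disaggregated by city and key demographic characteristics (age group and gender". Section 13.2 promises city-specific HIV indicators in the brief report.

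**The concern.** Section 4.4 offers ±8 points as the worst case for every indicator in every city. Section 4.3 says that better than ±10 points is out of reach at city level for an indicator limited to HIV-positive participants. Both statements cannot hold for viral suppression. The 4.4 sentence also comes soon after a calculation about viral suppression, so a reader will naturally take it to cover that indicator.

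Section 4.4 is the only place that gives city-level precision for 500 participants. Someone planning to use city cascade results, for example for the 95-95-95 monitoring in section 13.1, would expect estimates good to ±8 points. The design gives most of the cities that can be checked clearly less than that, and differences between cities could be given more weight than they deserve.

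**Working it through.** **Inputs.** From section 4.4: 500 per city, 5% missing, design effect 3.0, type I error 0.05 (z = 1.96), worst-case proportion 0.50. From the Annex on city selection: 2020 HIV prevalence. Denominators are from sections 4.3 and 9.6.

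**Step 1: the plan's city figure.** Analysable participants: 500 × 0.95 = 475. Half-width = 1.96 × √(3.0 × 0.25 / 475) = 0.078, or ±7.8 points (full width 15.6). This reproduces ~16% and 50±8%.

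**Step 2: the plan's cluster figure.** HIV-positive participants needed for 44±7%: 1.96² × 0.44 × 0.56 × 3.0 / 0.07² = 579.5. Dividing by prevalence and by completeness: 579.5 / 0.21 / 0.95 = 2905, against 2914 stated. The cluster calculation therefore already allows for the HIV-positive denominator.

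**Step 3: the city figure for indicators in HIV-positive participants.** Expected number m = 475 × prevalence. Half-width = 1.96 × √(3.0 × 0.25 / m).

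| City | 2020 prevalence (Annex) | m | Half-width, points | Ratio to 7.8 |
|---|---|---|---|---|
| Cherkasy | 34.6% | 164 | ±13.2 | 1.7 |
| Dnipro | 23.0% | 109 | ±16.2 | 2.1 |
| Planning value | 21% | 100 | ±17.0 | 2.2 |
| Odesa | 20.4% | 97 | ±17.2 | 2.2 |
| Kyiv | 16.6% | 79 | ±19.1 | 2.5 |
| Kharkiv | 7.1% | 34 | ±29.2 | 3.75 |

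The slightly higher prevalences in the 4.4 table give ±12.6 (Cherkasy), ±15.1 (Dnipro), ±16.9 (Odesa), ±18.3 (Kyiv) and ±28.4 (Kharkiv).

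**Step 4: sensitivity to the proportion and design effect.**
- Annex suppression values in place of 50%, design effect 3.0: Cherkasy (62.1%) ±12.8, Dnipro (33.0%) ±15.3, Odesa (42.1%) ±17.0, Kyiv (39.6%) ±18.7, Kharkiv (20.0%) ±23.4.
- Prevalence, suppression and each city's own suppression design effect from the 4.4 table: Cherkasy (86.5%, 1.61) ±6.3, Odesa (80.7%, 1.31) ±8.8, Kyiv (86.0%, 2.96) ±12.6, Dnipro (68.8%, 3.56) ±15.3. Kharkiv has no design effect in the table; keeping 3.0 with 90.9% gives ±16.4.
- City design effects at 50%, with m from step 3: Cherkasy 1.96 × √(1.61 × 0.25 / 164) = ±9.7; Odesa 1.96 × √(1.31 × 0.25 / 97) = ±11.4; Dnipro 1.96 × √(3.56 × 0.25 / 109) = ±17.7.

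**Step 5: the plan's own 2020 intervals.** In the 4.4 table, suppression in Dnipro is 68.8% (54.8 to 82.6), a half-width of (82.6 − 54.8) / 2 = 13.9 points. Kyiv, at 86.0% (77.0 to 95.0), has 9.0. Both proportions are away from 50%, so by the 4.4 sentence both should be narrower than ±8. The 2020 sample sizes are not stated. Back-calculated from the HIV prevalence intervals and design effects they are about 463 in Dnipro (1.96² × 2.78 × 0.265 × 0.735 / 0.067²) and 666 in Kyiv (1.96² × 3.27 × 0.182 × 0.818 / 0.053²). Samples far below 500 therefore do not explain the widths.

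**The case against.** The best defence is that the sentence is about 500 people and means what it says for 500 people: the reference to any indicator only explains why 50% was used. Section 4.3 has already warned that city-level suppression cannot be estimated tightly and gives this as the reason for clustering. Section 9.2 will print a confidence interval beside each estimate, so a reader of the results will see the true width. No test of cascade differences between cities is specified.

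Much of this stands. The arithmetic is right, the limitation is partly disclosed, and no sample size rests on the sentence. What does not stand is the narrow reading. The sentence expressly claims the worst case for any indicator, without limiting the denominator, and intervals in a later report do not correct a precision promised in the plan.

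The objection on magnitude also has force. The ±13 to ±29 range is for a proportion of 50% and design effect 3.0. Steps 3 and 4 show that it depends on inputs the protocol does not reconcile: Kharkiv suppression, for instance, is 90.9% in the 4.4 table and 20.0% in the Annex. With the table's values Cherkasy meets ±8. A reader might infer that every city misses ±8 for every such indicator, and the documents do not support that.

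**Conclusion.** The scope of the 4.4 statement is too wide. It holds for indicators measured in the full city sample. For viral suppression, status knowledge, registration and ART, the plan's own planning inputs give about ±17 points at 21% prevalence, and ±13 to ±29 across the five sentinel cities with 2020 data, or 1.7 to 3.75 times the stated width. This rests on 475 analysable, design effect 3.0, a proportion of 50% and Annex prevalences; the alternative inputs in the 4.4 table bring it down to about ±6 to ±16. The Kharkiv value is indicative only: 34 people at design effect 3.0 are an effective sample of about 11, too few for the simple formula.

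Three stronger readings are not supported:
- That the survey is too small for its main purpose. Step 2 shows that the cluster calculation allows for the HIV-positive denominator and is unaffected.
- That the whole cascade is affected. The first row in 9.6, PWID living with HIV, uses prevalence in the full sample.
- That the range describes all ten cities. The protocol gives no 2020 prevalence for Lviv or the additional cities.

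**What to change.** In section 4.4:

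1. Replace 'any indicator' with 'any indicator measured in the full city sample'.
2. Add that for indicators measured in HIV-positive participants the city-level half-width is about ±17 points at 21% prevalence. Illustrate this as ±13 to ±29 for the five sentinel cities with 2020 data, at a proportion of 50% and design effect 3.0, with the Kharkiv figure marked as indicative.
3. State, with a cross-reference to section 4.3, that city-level estimates of these indicators are descriptive and that the planned suppression precision of 44±7% applies to the sentinel cluster.

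The cost is two or three sentences and a less favourable stated figure. Sample size, data collection and analysis do not change. Enlarging the city samples is not the remedy: ±8 points at 50% among HIV-positive participants would need 1.96² × 0.25 × 3.0 / 0.08² = 450 of them, or 450.2 / 0.21 / 0.95 = 2256 participants in a city at 21% prevalence, which bears out section 4.3 on feasibility.

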For the trend analysis, assuming the HIV prevalence of 21%, the total sample (with N=629 living with HIV) will provide 80% power to detect a statistically significant increase in viral suppression from 44% (weighted average in sentinel cities in 2020) to 52% (and higher) in the next round, based on 0.05 probability of type I error (Figure).

¹¹ Appendix I-22: Sample Size Calculator for Survey-based Viral Load Suppression

¹² Centers for Disease Control and Prevention. National HIV Behavioral Surveillance System Round 5: Model Surveillance Protocol. December 11, 2018. Available from: www.cdc.gov/hiv/statistics/systems/nhbs/operations.html

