9.4 Trend analysis

To analyze the changes in key outcomes of interest across rounds, the final dataset may be merged with datasets from previous rounds. Only cities that participated in each analyzed round will be included. Combined weights (a product of RDS weight and city sample size weight OR the city population size, when becomes available) will be calculated and applied in the trend analyses. The significance of trend will be tested using two methods: (a) Mantel-Haenszel test of trend, used in the previous studies¹³, and (b) regression models with the survey round as an ordinal independent variable. Additionally, comparison between two consecutive rounds using Pearson's chi-square tests.

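### The 80% power stated for a rise in viral suppression from 44% to 52% matches a calculation without the design effect of 3.0 adopted in the same section; at 3.0 it is about 37%

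*Protocol*

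**What the plan says.** Section 4.4 estimates design effects from the 2020 survey and reports a range of 1.3 to 3.6 for viral suppression. It concludes: "Therefore, a conservative value of 3.0 is used for the following sample size calculation". The sentinel sample of 2,914 is then derived for a suppression estimate of 44±7%, with 21% HIV prevalence and 5% missing data. The city-level precision of 50±8% with 500 participants names the design effect of 3.0 explicitly.

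The trend-power statement closes the section. It opens "For the trend analysis, assuming the HIV prevalence of 21"%, says that "the total sample (with N=629 living with HIV) will provide 80% power to detect a statistically significant increase in viral suppression from 44"%, and describes the target as an "increase in viral suppression from 44% (weighted average in sentinel cities in 2020) to 52% (and higher) in the next round". It gives the type I error as 0.05 and points to a figure. It mentions neither a design effect nor whether the test is one- or two-sided.

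Two further passages bear on the baseline. Earlier in section 4.4, the 21% and 44% are described as a "combined weighted estimate using 2020 round data for 5 cities and 2017 data for Lviv". Section 9.4 (Trend analysis) says: "Only cities that participated in each analyzed round will be included". It also provides for RDS-based weights in the trend analyses and for Pearson chi-square tests between consecutive rounds.

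**The concern.** Precision and trend power are given in one section, for the same indicator and the same sentinel sample. The precision figures carry the variance inflation expected from respondent-driven sampling; the power figure appears not to. A design effect of 3.0 cuts 629 people to an effective 210 or so per round, too large a loss for the two statements to stand together.

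Section 4.3 ranks accurate trend monitoring at least as high as point estimates and keeps the sentinel cities fixed for later rounds on that ground. The power sentence is the protocol's only statement of what change the design can detect. A reader who relies on it could give a non-significant change between rounds more weight than the data can bear.

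**Working it through.** **Inputs from section 4.4.** p1 = 0.44; p2 = 0.52; n = 629 living with HIV (about 6 × 500 × 0.21 = 630); type I error 0.05; design effect 3.0, observed range 1.3 to 3.6. **Assumed, because not stated:** two-sided test; the same n and the same design effect (D) in both rounds.

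**1. Do the precision figures use 3.0?**
- Sentinel sample: 1.96² × 0.44 × 0.56 / 0.07² = 193.2. Then 193.2 × 3.0 / 0.21 / 0.95 = 2,905, against the stated 2,914. Without the design effect it would be about 968.
- City level: 1.96 × √(0.25 × 3.0 / 475) = 0.078, the stated ±8 points (475 = 500 × 0.95).

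Both do.

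**2. Reproducing the stated 80%.** For a two-sample comparison with mean proportion p̄ = 0.48:

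power = Φ{ [ (p2 − p1) − 1.96 × √(2p̄(1 − p̄)/n) ] / √[ (p1(1 − p1) + p2(1 − p2))/n ] }

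With n = 629 the two standard errors are 0.02817 and 0.02808, so power = Φ[(0.08 − 0.0552)/0.02808] = Φ(0.883) = 81.1%. The n for exactly 80% is 612 per round. A continuity correction gives 79.6%. The stated figure is reproduced with D = 1.

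**3. The same formula with D = 3.0.** Effective n = 629/3 = 209.7. The standard errors become 0.04879 and 0.04864, so power = Φ[(0.08 − 0.0956)/0.04864] = Φ(−0.321) = 37.4%. For 80% power at 44% versus 52%, 612 × 3 = 1,836 people living with HIV would be needed per round. With 629, the level detectable at 80% power is 57.6%, a rise of 13.6 points where the protocol states 8.

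**4. Across the section's range.**

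| Design effect | Two-sided power | One-sided power |
|---|---|---|
| 1.0 | 81% | 88% |
| 1.3 | 70% | 80% |
| 2.0 | 52% | 64% |
| 2.5 | 43% | 56% |
| 3.0 | 37% | 50% |
| 3.6 | 32% | 44% |

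**5. A one-sample test against a fixed 44%.** Two-sided power is 98% at D = 1, 81% at D = 2 and 64% at D = 3.

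**6. If the contrast is 2020 to 2023.** The Annex shows no 2020 values for Lviv, so section 9.4 leaves five sentinel cities. The Annex prevalences at 500 per city give 500 × (0.230 + 0.204 + 0.071 + 0.346 + 0.166) ≈ 508 people living with HIV, or about 483 after 5% missing data. If both rounds had roughly 485 to 510, power at D = 3.0 would be 30% to 31%. The 2020 counts are not in the protocol, so this is an assumption.

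**The case against.** **The setting behind the 80% cannot be seen.** The figure cited for the calculation is not shown, and sidedness is not stated. A reader might infer that 80% can arise only with a design effect of 1. That is too strong: a one-sided two-sample test at 1.3 gives 80%, and a one-sample test at 2.0 gives 81%. The text supports neither, since it adopts 3.0 and section 9.4 plans comparisons between rounds. Omission of the design effect is therefore the likeliest explanation, but an inferred one. At 3.0 none of these tests reaches 80%.

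**37% is one point in a range.** The protocol itself calls 3.0 conservative. The section's suppression design effects for four sentinel cities (3.56, 2.96, 1.31 and 1.61; none is given for Kharkiv) average 2.36, which gives about 46%. They also belong to suppression estimates of 69% to 87%, whereas the 44% indicator corresponds to the lower values in the Annex, so how well they carry over is uncertain. This stands, and is a reason to report the range. It does not bring two-sided power to 80%.

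**The practical consequence depends on the test.** One might conclude that a true 8-point gain would be missed about six times in ten. That assumes a test adjusted for the design, which section 9.4 does not specify for the two-round chi-square. An unadjusted test at 3.0 would have power Φ[(0.08 − 0.0552)/(√3 × 0.02808)] = 69%, missing about three in ten, but its type I error would be 2Φ(−1.96/√3) = 26%, not 5%. Section 9.4 also lists this test as additional to the trend tests across rounds.

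**Lviv may not matter.** If the next round means the one after 2023, all six sentinel cities are in both rounds and section 9.4 excludes none. The sentence nevertheless ties its 44% to 2020, so the text is ambiguous. Five-city power of 30% is not an established result.

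**Nothing else rests on the power figure.** The sample size comes from precision. This is correct and limits the remedy to wording.

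**Conclusion.** The trend power in section 4.4 is wrong as written. It agrees with a two-sided comparison of two rounds of 629 under simple random sampling (81%) and conflicts with the design effect of 3.0 adopted a few lines earlier. At 3.0, power for 44% to 52% is about 37%, and the increase detectable with 80% power is from 44% to about 58%. Over design effects of 1.3 to 3.6, power is about 70% to 32%.

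This rests on a two-sided test and on equal numbers and design effects in both rounds. The main conclusion survives a change of sidedness at 3.0, where one-sided power is 50%. The Lviv point is secondary and applies only if the rounds meant are 2020 and 2023. A reader might also infer that the survey is too small; the documents do not support that, because the sample was sized for precision with the design effect included.

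**What to change.** Replace the power sentence in section 4.4 with wording such as: *Allowing for a design effect of 3.0, the sentinel sample gives 80% power (two-sided 0.05) for an increase from 44% to about 58%; power for 44% to 52% is about 37% (32–70% over design effects of 3.6–1.3).* Bring the accompanying figure into line, and state the assumption of equal numbers and design effects in both rounds.

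Name the two rounds being compared. If they are 2020 and 2023, say that the comparison covers five sentinel cities without Lviv, and give its power from the actual 2020 counts of HIV-positive participants.

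The cost is protocol wording and a less favourable stated power. Sample size, sites and procedures stay as they are.

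### The 80% power for a rise in viral suppression from 44% to 52% leaves out the design effect of 3.0 adopted in the same section; with it, power is about 36-38%

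*Protocol*

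**What the plan says.** Section 4.4 tabulates design effects by city from the 2020 round and summarises those "for viral suppression from 1.3 to 3.6". It continues: "Therefore, a conservative value of 3.0 is used for the following sample size calculation". Two precision results follow. One is a sentinel-cluster sample of 2914 for 44±7% viral suppression, at 21% HIV prevalence with 5% missing data. The other is a city-level precision of 50±8% from 500 participants, explicitly with a design effect of 3.0 and 5% missing data.

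The power statement comes next. At 21% prevalence and a type I error of 0.05, the total sample, put at 629 HIV-positive people, "will provide 80% power to detect a statistically significant increase in viral suppression from 44% (weighted average in sentinel cities in 2020) to 52" percent or more by the following round. It mentions neither a design effect nor missing data, and does not say whether the test is one- or two-sided.

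Section 9.4 says that combined weights, which include the RDS weight, will be applied in trend analyses, and that consecutive rounds will be compared with Pearson chi-square tests.

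**The concern.** The 629 is essentially the raw expected count: 21% of the 3,000 participants in six sentinel cities is 630. It has not been reduced for the variance inflation of respondent-driven sampling or for the 5% loss, although the section allows for both in the two results just before. Because the trend analyses use RDS weights, the inflation applies to the comparison between rounds as well.

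Section 4.3 ranks accurate trend monitoring no lower than point estimates and fixes the sentinel cities for future rounds on that ground. A reader who trusts 80% power would take a non-significant change as fair evidence against an 8-point gain. At the adopted design effect, a design-adjusted two-sided test would miss a true gain of that size more than 60% of the time.

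**Working it through.** **Inputs, all from section 4.4:** p1 = 0.44, p2 = 0.52, n = 629, alpha = 0.05, design effect (DE) = 3.0, missing data 5%, prevalence 21%. **Assumptions:** two-sided alpha and the same n in both rounds.

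**1. The precision figures do contain DE = 3.0.**
- Cluster: 1.96² × 0.44 × 0.56 / 0.07² = 193.2; × 3 / 0.21 / 0.95 = 2,905, against the stated 2914. With DE = 1 the result would be about 968.
- City: 1.96 × sqrt(3 × 0.25 / 475) = 0.078, the stated ±8 points. With DE = 1 it would be ±4.5 points.

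**2. Reproducing the stated 80%.** Take z = (p2 − p1) / sqrt(DE × [p1(1 − p1) + p2(1 − p2)] / n) and power = Φ(z − 1.96). The bracket is 0.2464 + 0.2496 = 0.496. At DE = 1 and n = 629, z = 0.08 / 0.02808 = 2.849 and power is 81.3%. Pooled-variance and arcsine versions give 81.1%, and the continuity-corrected version 79.6%. The stated figure is therefore matched with no design effect.

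**3. The same formula with a design effect.** Missing data reduce 629 to 629 × 0.95 ≈ 598.

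| DE | Source | n per round | z | Power |
|---|---|---|---|---|
| 1 | none applied | 629 | 2.849 | 81.3% |
| 1.31 | lowest viral-suppression value (Odesa) | 629 | 2.489 | 70.2% |
| 2.36 | mean of four sentinel cities | 629 | 1.855 | 45.8% |
| 3.0 | adopted value | 629 | 1.645 | 37.6% |
| 3.56 | highest value (Dnipro) | 629 | 1.510 | 32.6% |
| 1 | none applied, 5% missing | 598 | 2.778 | 79.3% |
| 3.0 | adopted value, 5% missing | 598 | 1.604 | 36.1% |

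The mean is (3.56 + 2.96 + 1.31 + 1.61) / 4 = 2.36, for Dnipro, Kyiv, Odesa and Cherkasy. Kharkiv has no value and Lviv is not in the table.

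**4. Detectable rise at 80% power with DE = 3.0.** Solve p2 − 0.44 = (1.96 + 0.8416) × sqrt(3 × [0.2464 + p2(1 − p2)] / n). This gives p2 = 0.576 for n = 629 and 0.579 for n = 598, a rise of 13.6 to 13.9 points rather than 8. The effective sample sizes are 629 / 3 ≈ 210 and 598 / 3 ≈ 199 per round.

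**5. Number needed for 52%.** At DE = 1, 80% power needs about 608 per round (612 with pooled variance). At 3.0 that becomes 3 × 612 = 1,836 people living with HIV per round, or 1,836 / 0.21 ≈ 8,740 participants.

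**6. Other readings at DE = 3.0, n = 629.** A two-sample one-sided test has 50% power (48% with 5% missing). Treating 44% as a fixed known value gives 64.5% two-sided and 75.3% one-sided. None reaches 80%.

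**The case against.** - **The omission is inferred.** The cited figure is not shown and may state its assumptions. That is true, but the text fixes n, both proportions, alpha and power, and the standard calculation returns 80% without a design effect. A one-sided two-sample test at a design effect of 1.3 also gives 80.2%. It needs an unstated one-sided test and the most favourable city's value, and it contradicts the adopted 3.0.
- **The replacement figure is conditional.** The protocol itself calls 3.0 conservative, and two-sided power at n = 629 runs from about 70% to 32% over the reported range. This stands as a reason to report the range. It does not rescue 80%.
- **The 2.36 average is weak.** It covers four of six sentinel cities, and an unweighted mean of city values is not a pooled-cluster design effect. The tabulated values also accompany suppression estimates of 69-91%, whereas the power target starts at 44%. This stands, so the 46% is only illustrative. The main conclusion uses 3.0 and does not depend on it.
- **The consequence depends on the test.** An unadjusted chi-square test, with true DE = 3.0, would reject in about 70% of surveys when the rise is real: Φ((2.849 − 1.96) / 1.732). It would also reject in about 26% when there is no change: 2 × [1 − Φ(1.96 / 1.732)]. The statement about missed gains therefore presumes a design-adjusted two-sided test. That is accepted; the higher rejection rate is not valid power at 0.05.
- **More cities could be compared.** All ten would give 5,000 × 0.21 = 1,050 people living with HIV and about 56% power at 3.0. The stated 629 fits the six sentinel cities, and 56% is still well short of 80%.
- **Enrolment does not rest on this sentence.** Correct: the sample size comes from precision. That limits the fix to wording and a figure, but the stated power is still wrong.

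**Conclusion.** The concern holds. The 80% agrees with the standard calculation only when the design effect adopted in the same section is left out. At 3.0, with two-sided alpha 0.05 and equal rounds of 629, power for 44% to 52% is about 38%, or about 36% after 5% missing data. The claim is overstated roughly twofold, and the rise detectable with 80% power is to about 58%. The exact replacement value depends on the design effect, sidedness and equal round sizes. The direction does not: two-sided power at n = 629 stays below 80% at every viral-suppression design effect in the protocol's table, and no variant tried at 3.0 reaches it. Because a number stated in the protocol is wrong on its own inputs, it must be corrected.

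**What to change.** Restate the power sentence in section 4.4. With a design effect of 3.0, 5% missing data, two-sided alpha 0.05 and equal sentinel-cluster rounds, power is about 36% for a rise from 44% to 52%, and 80% power is reached only for a rise to about 58% or more. State the number living with HIV assumed in each round, and that the power refers to a test that accounts for the design. Adding power at the ends of the reported design-effect range would show how far the result depends on 3.0. Redraw the power figure on effective sample sizes of about 199-210 per round.

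The cost is protocol wording and one figure, with a less favourable power claim. Enrolment and survey procedures are unchanged.
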